## 1 Introduction

This document is a clinical investigation plan (CIP) to evaluate the sustainability of pain control utilizing a multiple-waveform enabled neurostimulator in patients with chronic, intractable pain of the trunk and/or limbs. This clinical investigation is sponsored by Abbott (formerly St. Jude Medical) and will be conducted in accordance with this CIP.

## 2 Background and Justification for Clinical Investigation

Spinal cord stimulation (SCS) is a minimally invasive and reversible procedure in which electrical leads are placed into the epidural space, applying stimulation to the large myelinated fibers of the dorsal column. SCS has been used successfully to treat a variety of pain conditions including, diabetic neuropathy , failed back surgery syndrome , complex regional pain syndrome , phantom limb pain , ischemic limb pain , refractory unilateral limb pain syndrome , postherpetic neuralgia and acute herpes zoster pain .

A systematic review and meta-analysis of SCS in refractory neuropathic back and leg pain  documented that SCS reduces pain, improves quality of life, reduces analgesic use, allows some patients to return to work, and may also result in significant cost savings over time with minimal significant adverse events.

Historically, SCS has delivered a tonic stimulation pattern where impulses are delivered at a consistent amplitude, frequency, and pulse width, typically producing paresthesia (tingling sensation) over the patient's area of pain. A variety of amplitudes, frequencies, and pulse widths can be programmed along with an option to turn the stimulation on and off throughout the day (known as Cycle Mode). However, recent technical developments provide expanded stimulation options. St. Jude Medical developed the Prodigy (MRI)TM and Proclaim EliteTM systems, both of which are capable of producing either tonic stimulation (see Figure 1) or BurstDRTM stimulation (Figure 2).

BurstDR stimulation features a series of impulses in rapid succession, known as a burst train, followed by a short silent phase. Programmable parameters include the amplitude of the burst train, the time from onset of one burst train to the onset of the next burst train (burst rate), and the rate of pulses within each train (intra-burst rate) (See Figure 2). BurstDR is thought to improve SCS effectiveness by mimicking the natural burst firing patterns found in the brain . Amplitudes programmed for BurstDR are typically lower than those traditionally used for tonic stimulation, often resulting in pain suppression without paresthesia.

Previous studies using BurstDR have examined the safety and efficacy of the stimulation mode for patients who were already using tonic stimulation . These studies reported favorable outcomes for the new stimulation mode, with many patients achieving greater pain control and experiencing less paresthesia with BurstDR compared to tonic stimulation. Currently, the body of evidence for BurstDR is limited to subjects with prior experience using tonic stimulation. Patients who trial the SCS system with tonic stimulation may be conditioned to associate paresthesia with pain relief. When the patient then switches to BurstDR stimulation, the lack of paresthesia may violate that previous association and reduce the potential benefit of treatment. The SUNBURST trial  provides some evidence that this may be the case. In the trial, BurstDR stimulation was shown to provide more pain relief than tonic stimulation, but 22% of the patients who failed to achieve at least 30% pain reduction with BurstDR did achieve clinically relevant pain relief with tonic stimulation. It is possible that these patients would have responded to BurstDR had they not previously been conditioned to tonic stimulation. Data regarding patients who use BurstDR stimulation from the beginning of their exposure to SCS is necessary to fully evaluate any qualitative or quantitative differences in therapy outcomes for the two waveforms.

The SUNBURST trial in the US and PRODIGY I PMCF in Europe demonstrated clinically meaningful pain reduction with BurstDR at one year; however, no studies to date have reported outcomes beyond 12 months. Longer-term follow-up is needed to demonstrate sustainable pain relief over time.

For devices that deliver both tonic and BurstDR waveforms, individual patient characteristics (e.g. pain history, mental/physical health, and sensory experience) may affect the way a patient achieves maximum

benefit from the therapy. After an initial crossover period, SUNBURST allowed patients to select the program mode (tonic or BurstDR) according to individual preference during the follow-up period. Approximately 60% of subjects used BurstDR most frequently at one year, while the other 40% used some combination of tonic and BurstDR programs. The relationships between program usage patterns, patient characteristics, and long-term outcomes have yet to be examined for these multi-waveform SCS devices. Exploring these relationships will likely provide valuable insight into patient needs and enhance clinical care decisions.

Given the evidence gaps described above for BurstDR and multi-waveform devices, the goals of the current study are: to assess pain relief for BurstDR stimulation when presented as the initial SCS experience, assess long-term outcomes for BurstDR, and to explore the relationship between program usage patterns, patient characteristics, and therapy outcomes.

Figure 1: Tonic pattern

[figure not shown]
[figure not shown]

Figure 2: BurstDR pattern

### 3 Device(s) Under Investigation

#### 3.1 Identification and Description of the Devices under investigation

Table 1: Identification of Devices under Investigation

Device Type	Device name	Model/ Type	Description	Investigational or Market Released
Trial System	SJM Invisible Trial System	3599 & 3032	
The SJM Invisible Trial™ System is an external pulse generator (model 3599) with disposable header (model 3032) that connects to, and is compatible with, commercially available SJM trial leads and extensions. It provides electrical stimulation to nerve structures either intraoperatively or post-operatively during a trial system evaluation period. The External Pulse Generator (EPG) can support up to 16 active electrodes.
 
Stimulation settings are wirelessly programmed securely over Bluetooth using the Clinician Programmer and stored on the EPG.
 
Batteries support a 14-day trial system evaluation period and the EPG also supplies diagnostics that can provide the user additional data regarding the neurostimulation trial.
 
A complete description and illustration of use are provided in the External Pulse Generator Clinician's Manual.
	Market Released
Trial System	Multiprogram Trial Stimulator® (MTS) - can only be used for on- the-table trials.	3510	The Multiprogram Trial Stimulator System (MTS) is a programmable device designed to deliver low-intensity electrical impulses to nerve structures in the dorsal aspect of the spinal cord. The system consists of an external stimulator, one or two trial cables, and percutaneous leads. The stimulator is a small, battery-powered, external device that delivers electrical impulses through the trial cable to the implanted lead(s). It contains electronic circuitry that allows the stimulator to be easily programmed with different stimulation settings for versatile pain control therapy.	Market Released
IPG	Proclaim Elite 5 IPG & Proclaim Elite 7 IPG	3660 & 3662	This Implantable Pulse Generator (IPG) is an electronic device designed to be connected to one or more extensions or leads with up to 16 electrodes in total. It is powered by a hermetically sealed battery within a titanium case and uses microelectric circuitry to generate constant-current electrical stimulation. The IPG can be programmed with multiple stimulation options. Each program can provide stimulation to a single anatomical area or to multiple areas, using either a tonic or BurstDR waveform. The IPG communicates wirelessly with	Market Released

*This confidential document is the property of Abbott and shall not be reproduced, distributed, disclosed or used without the express written consent of Abbott.*

## Clinical Investigation Plan

			
the system programmer and controller, and IPG's are available in small (3660) and large (3662) sizes to accommodate different power needs. These models can receive software upgrades after implantation to provide patients with additional features as approved by the respective regulatory agencies.
 
A complete description and illustration of use are provided in the Clinician's manual of the Proclaim Elite IPG.
	
IPG	Prodigy IPG	3799	
The Prodigy IPG is a rechargeable, electronic device designed to be connected to one or more leads. It is powered by a hermetically sealed battery within a titanium case and uses microelectronic circuitry to generate constant current electrical stimulation. The IPG can deliver stimulation with a range of waveforms (called MultiStim™) depending on the individual patient's need. Prodigy is enabled to deliver both tonic and BurstDR stimulation.
 
A complete description and illustration of use are provided in the Clinician's manual of the Prodigy IPG
	Market Released
IPG	Prodigy MRI IPG	3772	
The Prodigy MRI IPG is a rechargeable, electronic device designed to be connected to one or more leads. It is powered by a hermetically sealed battery within a titanium case and uses microelectronic circuitry to generate constant current electrical stimulation. The IPG can deliver stimulation with a range of waveforms (called MultiStim) depending on the individual patient's need. Prodigy MRI is enabled to deliver both tonic and BurstDR stimulation and is conditionally approved for Magnetic Resonance Imaging (MRI) scans only when they meet the requirements.
 
A complete description and illustration of use are provided in the Clinician's manual of the Prodigy MRI.
	Market Released

## Clinical Investigation Plan

Clinician Programmer	SJM Clinician Programmer for Invisible Trial System and Proclaim Elite 5 and 7	3872	
The Clinician Programmer is a tablet-based programmer (iPad mini) that controls the creation and adjustment of all programming information for the SJM Invisible Trial EPG and Proclaim Elite IPG. The software is an iPad mini app with model number 3870 (for EPG) and 3874 (for IPG) or subsequent updates that runs on a standard commercial Apple iPad mini. The Clinician Programmer communicates with the EPG and IPG using Bluetooth Low Energy (BLE) technology. As with past SJM programmer models, this Clinician Programmer enables users to create and modify stimulation programs.
 
A complete description and illustration of use are provided in the Clinician Programmer Clinician's Manual.
	Market Released
Clinician Programmer	Rapid Programmer System for Prodigy (MRI)	3835 & 3834	
The Rapid Programmer™ is intended to help clinicians determine the best performance of a neuromodulation system by leading the physician through a series of parameter combinations for the neuromodulation system and recording the stimulation effects. The device is intended to be used for programming the Prodigy (MRI) device while it is disconnected from an external power source. The clinician programming external device allows activation of BurstDR programs in addition to traditionally available tonic programs.
 
A complete description and illustration of use are provided in the Clinician's manual of the Rapid Programmer system.
	Market Released
Patient Controller	Patient Controller (iPod touch) for the Invisible Trial System	3873	
The Patient Controller is a simplified controller that enables adjustment of pre-specified programming information for the SJM Invisible Trial System. The software is an iPod touch app with model number 3871 that runs on a standard commercial Apple iPod touch using BLE technology. As with past SJM controller models, this Patient Controller enables users to adjust stimulation programs.
 
A complete description and illustration of use are provided in the Patient Controller User's Guide.
	Market Released

Patient Controller	iPod touch Mobile Digital Device for Proclaim Elite 5 & 7	3883	
The Patient Controller is a simplified controller that enables adjustment of pre-specified programming information for the Proclaim Elite IPG. The software is an iPod touch app with model number 3875 that runs on a standard commercial Apple iPod touch using BLE technology. As with past SJM controller models, this Patient Controller enables users to adjust stimulation programs.
 
A complete description and illustration of use are provided in the Patient Controller User's Guide
	Market Released
Patient Controller	Prodigy (MRI) patient programmer for Prodigy and Prodigy MRI	3855 & 3856	
The Prodigy (MRI) patient programmer controls the creation and adjustment of all programming information for the Prodigy IPG (3855) and Prodigy MRI (3856). The device communicates by using radiofrequency (RF) signals from the programming wand to the implanted IPG. The device enables clinicians to create and modify programs for the IPG. It also provides patients with Patient-Controlled Stimulation technology, which enables them to choose between several prescribed programs stored in the device's memory. The Prodigy (MRI) Patient Controller External Device introduces the ability for a patient to select (an) existing BurstDR program(s) in addition to traditionally available tonic program(s).
 
A complete description and illustration of use are provided in the Prodigy (MRI) patient programmer user's guide.
	Market Released
	Prodigy (MRI) Charging System	3730	
The Prodigy (MRI) Charging System provides the capability to recharge the IPG battery while stimulation is either on or off. The system consists of a charger, antenna, power adapter, and power cable. The charger transmits RF energy through the antenna to the IPG battery to recharge it.
 
A complete description and illustration of use are provided in the Prodigy (MRI) Charging system user's guide.
	Market Released
	Leads/Extensions /Accessories		
Any compatible and commercially available lead/extension and accessory may be used in the study.
	Market Released

### 3.1.1 Device Description and Intended Purpose

In this study, the commercially available St. Jude Medical Invisible Trial System will be used according to the Instructions for Use (or any other SJM EPG system with BurstDR form functionality when available and approved for use). For on-the-table trials (when the trial system evaluation and permanent implant are done during the same procedure) only, the MTS can be used according to the Instructions for Use.

In this study, any commercially available Prodigy (MRI) neurostimulation system or Proclaim Elite system will be used according to the Instructions for Use (or any other SJM spinal cord stimulation system with both tonic and BurstDR form functionality when available and approved for use).

Both Prodigy (MRI) and Proclaim Elite neuromodulation systems are indicated as an aid in the management of chronic, intractable pain of the trunk and/or limbs.

### **3.1.2 Device Handling and Storage**

The devices used during this study are commercially available and will be handled and stored according to the applicable product manuals and standard site practices.

## **4 Clinical Investigation Design**

### **4.1 Clinical Investigation Design**

The study is designed as a post-market, international, multicenter, interventional, prospective, single-arm study. The purpose of this clinical study is to examine pain relief and other outcomes for subjects with chronic, intractable pain of the trunk and/or limbs who use BurstDR stimulation during the trial evaluation period and at 6, 12, 18 and 24 months after permanent system implant. Furthermore, the study seeks to explore sustainable pain relief, psychological outcomes, and stimulation usage patterns with a device capable of delivering multiple stimulation modes (BurstDR and tonic) through 24 months post-permanent implant. Finally, this study will collect MRI safety information, when available, for enrolled patients.

The investigation will be conducted in approximately 30 centers in EMEA, US, Canada and ANZ. Estimated enrollment duration is approximately 18 months with 24 months follow-up. Approximately 267 subjects will be enrolled in the study. A maximum of 53 subjects can be included per center. The study may continue up to 4 years, dependent on the rate of enrollment (approximately 18 months enrollment + 24 months follow-up + time to close the investigation and provide final report).

### **4.2 Objectives**

#### **4.2.1 Primary Objectives**

The primary objective is to evaluate pain relief in subjects with a multiple-waveform enabled neurostimulator.

#### **4.2.2 Secondary Objectives**

The secondary objectives are to evaluate the psychosocial and functional responses in subjects with a multiple-waveform enabled neurostimulator.

### **4.3 Endpoints**

#### **4.3.1 Primary Endpoint**

The primary endpoint is change from baseline to 6 months post-permanent implant in pain assessed by using the Numeric Rating Scale (NRS).

#### 4.3.2 Secondary Endpoint

- Change from baseline to 6 months post-permanent implant for quality of life measured using the EuroQuol -5 Dimensions (EQ5D) questionnaire.
- Change from baseline to 6 months post-permanent implant for pain catastrophizing measured using the Pain Catastrophizing Scale (PCS).
- Change from baseline to 6 months post-permanent implant for anxiety measured using the State-Trait Anxiety Inventory (STAI).
- Change from baseline to 6 months post-permanent implant for depression measured using the Patient Health Questionnaire-9 (PHQ9).
- Change from baseline to 6 months post-permanent implant for fear avoidance measured using the Tampa Scale for Kinesiophobia (TSK).
- Change from baseline to 6 months post-permanent implant for sleep measured using the Medical Outcome Study (MOS) Sleep Scale.
- Change from baseline to 6 months post-permanent implant for physical function measured using the Patient-Reported Outcome Measure Information System (PROMIS) Physical Function Scale.

#### 4.3.3 Demographic/Baseline Characteristic and Descriptive Endpoint(s)

- Change from baseline to 12, 18 and 24 months post-permanent implant for quality of life measured using the EQ5D questionnaire.
- Change from baseline to 3, 12, 18, and 24 months post-permanent implant for pain catastrophizing measured using the PCS.
- Change from baseline to 12, 18 and 24 months post-permanent implant for anxiety measured using the STAI.
- Change from baseline to 12, 18 and 24 months post-permanent implant for depression measured using the PHQ9.
- Change from baseline to 3, 12, 18 and 24 months post-permanent implant for fear avoidance measured using the TSK.
- Change from baseline to 12, 18 and 24 months post-permanent implant for sleep measured using the MOS Sleep Scale.
- Change from baseline to 12, 18 and 24 months post-permanent implant for physical function measured using the PROMIS Physical Function Scale.
- Change from baseline to End of Trial system evaluation 3, 12, 18, and 24 months post-permanent implant in pain assessed by using the NRS.
- Demographics and baseline characteristics.
- Patient waveform preference (if applicable).
- Patient satisfaction at End of Trial system evaluation 3, 6, 12, 18, and 24 months post-permanent implant.
- Global improvement of the patient by using the Patient Global Impression of Change (PGIC) at End of Trial System Evaluation 3, 6, 12, 18, and 24 months.
- Medication usage measured in decrease in chronic pain related medication intake since baseline at 3, 6, 12, 18, and 24 months post-permanent implant.
- Battery consumption and/or recharging activities.
- Stimulation Assessment measured by using the Stimulation Assessment Form at 3, 6, 12, 18, and 24 months post-permanent implant as well as any unscheduled visit where reprogramming occurs.
- Program information including amplitude, pulse width, frequency and electrode configuration.
- System information including device type, model number, serial number and number of leads.
- Proportion of device, or procedure-related Serious Adverse Events (SAE)'s and non-serious adverse events in subjects who receive permanent implant of the SCS system.

## 4.4 Study Population

The patient population enrolled in this study will be comprised of male and female patients. Patients must meet the specific eligibility criteria to participate in the study.

A patient, who meets all inclusion criteria, and none of the exclusion criteria, is eligible to participate in this study.

### 4.4.1 Inclusion Criteria

1. Subject has chronic, intractable pain of the trunk and/or limbs, including unilateral or bilateral pain associated with the following: failed back surgery syndrome and intractable low back and leg pain.
2. Subject has a score of 6 or higher on the NRS for average pain specific to the area(s) of chronic pain being treated over the past 24 hours at the baseline visit.
3. Subject is considered by the Investigator as a candidate for implantation of a spinal cord stimulator system according to the system Instructions for Use.
4. Subject is 18 years of age or older at the time of enrollment.
5. Subject is willing to cooperate with the study requirements including compliance with the regimen and completion of all study visits.
6. Subject has signed and received a copy of the Ethics Committee/Institutional Review Board (EC/IRB) approved informed consent.

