### **5.3.2 Trial System Implant**

(In clinic, prior to permanent implantation, within 3-45 days from Baseline visit)

Subjects must undergo a successful trial system evaluation of the SCS system prior to permanent implantation of the SCS system. It is a requirement that the subjects will be trialed with BurstDR and only a BurstDR program will be provided to, and used by, the subject. In case of an on-the-table trial evaluation (aka all-in-one procedure), the pain mapping can be done with tonic. The trial system evaluation procedure will be conducted according to the national standards and guidelines. The SCS Trial System Evaluation visit will include recording the following:

- Trial System implant and system information
- Adverse Events (if applicable)
- Deviations (if applicable)
- Withdrawal (if applicable)
- Death (if applicable)

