#### **5.4.8 Pain Numerical Rating Score (NRS)**

The pain NRS consists of 1 question that will be asked by interviewing the subjects. Patients will be asked to rate, from 0 (no pain) to 10 (worst imaginable pain), their average pain over the past 24 hours specific to the area(s) of chronic pain being treated. A higher score indicates greater pain intensity.

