
## 6 Statistical Considerations

### 6.1.1 Primary Endpoint

The analysis population will include subjects who complete the NRS at both baseline and 6-month follow-up visit. The primary endpoint will be calculated as follows:

Change in pain = pain at 6 months assessed by NRS – pain at baseline assessed by NRS  
Relative Change in pain (%) = (change in pain at 6 months/pain at baseline assessed by NRS)\*100%

Change and relative change (%) in pain will be summarized by mean and standard deviation, median, minimum, maximum and a 95% confidence interval. Results will be descriptively compared to data from existing tonic and BurstDR trials to evaluate efficacy.

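### One NRS reading of 6 or higher both qualifies the subject and serves as the primary-endpoint baseline in a single-arm study, so regression to the mean is counted as pain relief

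*Combined protocol and SAP*

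**What the plan says.** Inclusion criterion 2 (section 4.4.1) requires that "Subject has a score of 6 or higher on the NRS for average pain specific to the area(s) of chronic pain being treated", and the score is the average "over the past 24 hours at the baseline visit". Section 5.4.8 describes the instrument: "The pain NRS consists of 1 question that will be asked by interviewing the subjects".

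Section 5.3.1 lists the NRS once at baseline. Table 2 (section 5.6) shows no other NRS before the trial system is implanted; the next is at the end of the trial evaluation. Section 6.1.1 (Primary Endpoint) defines the outcome as "Change in pain = pain at 6 months assessed by NRS – pain at baseline assessed by NRS" and divides by the same baseline for the relative change. Section 6.1.3 measures NRS change from baseline at the end of the trial and at 3, 12, 18 and 24 months.

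The design is single-arm (sections 4.1 and 6.2). The primary result is a descriptive summary with a 95% confidence interval, compared descriptively with existing tonic and BurstDR trials as evidence on efficacy. The plan has no run-in, repeated or averaged baseline, separate qualifying score or adjustment for regression to the mean.

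**The concern.** A single 24-hour pain rating mixes the patient's usual level with day-to-day variation. A threshold of 6 preferentially admits patients whose variation was upward that day. Their later scores drift back, and the endpoint records the drift as improvement. The direction is fixed whenever the threshold turns some patients away and the correlation between readings is below 1.

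Two things are at stake. The sample size in section 6.3 is justified only by the precision of this interval, and the interval measures sampling error, not bias; more subjects narrow it around the shifted value. The shifted estimate also enters the comparison with existing trials, and the same baseline feeds every other NRS change.

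**Working it through.** **The plan's own figures (section 6.3).**
- Implanted: 267 × 0.90 × 0.70 = 168.2.
- Evaluable: 168.2 × 0.86 = 144.7, stated as 145.
- Standard error with the assumed SD of 3: 3/√145 = 0.249.
- Half-width: 1.96 × 0.249 = 0.488, or 0.492 with the t quantile on 144 df. The stated 0.49 is reproduced.

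**Inputs for the artefact.** From the documents: threshold 6 on a 0 to 10 scale, one reading, no control. Assumed, because the documents give none of them: screening mean μ of 6 to 7.5, SD σ of 1.5 to 2.0, and correlation r of 0.6 to 0.9 between the entry reading and the 6-month reading.

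**Formula.** With normal scores and no treatment effect, the expected fall is (1 − r) × σ × λ, where λ = φ(a)/(1 − Φ(a)) and a = (5.5 − μ)/σ. The cut is 5.5 because scores are whole numbers. A simulation with scores rounded and limited to 0 to 10, entry at 6 or higher and no treatment effect gives slightly larger values:

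| μ | σ | r | λ | Formula | Simulated fall |
|---|---|---|---|---|---|
| 7.5 | 1.5 | 0.9 | 0.18 | 0.1 × 1.5 × 0.18 = 0.03 | 0.04 |
| 7 | 1.8 | 0.8 | 0.35 | 0.2 × 1.8 × 0.35 = 0.13 | 0.14 |
| 6.5 | 1.8 | 0.8 | 0.48 | 0.2 × 1.8 × 0.48 = 0.17 | 0.20 |
| 6.5 | 1.8 | 0.6 | 0.48 | 0.4 × 1.8 × 0.48 = 0.35 | 0.37 |
| 6 | 2.0 | 0.6 | 0.65 | 0.4 × 2.0 × 0.65 = 0.52 | 0.54 to 0.55 |

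The middle three rows span the central cases, 0.14 to 0.37. At r = 0.5 with mean 6 and SD 2.0 the fall reaches 0.67.

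**Effect on the interval.** With SE 0.249, coverage of the true mean change under a bias b is Φ(1.96 − b/SE) − Φ(−1.96 − b/SE). For b = 0.20 this is about 87%, and for b = 0.37 about 68%, instead of 95%.

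**Effect of a second reading.** If the second pre-treatment reading becomes the baseline, the remaining bias is (r_short − r_long) × σ × λ. Here r_short is the correlation between the two pre-treatment readings, and r_long is that of either with the 6-month reading. If they are equal, the bias is about 0.00. At mean 6.5 and SD 1.8, simulation gives:
- r_short 0.9, r_long 0.6: 0.37 falls to 0.26.
- r_short 0.8, r_long 0.6: 0.37 falls to 0.17.
- r_short 0.9, r_long 0.8: 0.20 falls to 0.09.

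These calculations isolate the entry threshold. They do not model the further selection of trial-system successes and 6-month completers.

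**The case against.** The strongest reply is that the effect is small and the endpoint descriptive. Much of that stands. Every size above rests on assumed inputs. Section 2 uses a 30% reduction as a benchmark, which from a score of 6 is 1.8 points, well above any value in the table. A reader might infer that regression to the mean could account for the relief the study reports; the documents do not support that. A reader might also treat 0.49 as a margin that the bias could use up. The plan has no margin, hypothesis test or success criterion; 0.49 is a projected half-width, and over correlations of 0.6 to 0.9 the artefact exceeds it only near the corner with mean 6, SD 2.0 and correlation 0.6. No type I error is affected.

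A second reply is that the existing trials may carry the same artefact, so that it partly cancels. It would, if they used a similar threshold and single-reading baseline. The plan neither states nor requires this, so bias in that comparison is not established either way.

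A third is that a second reading may correct only part of the bias and may come late. Both parts are fair. The second reading would fall "prior to permanent implantation, within 3-45 days from Baseline visit", much closer to the first reading than to the 6-month one. The plan was first released in May 2015, the current version is dated November 2018, and enrolment was expected to take about 18 months. Enrolment status is not stated. This is why the sensitivity analysis is needed as well.

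What does not yield is the structure: the plan counts this drift as relief, and its interval does not reflect it.

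**Conclusion.** The point holds as a modest bias of known direction and unknown size. It rests on one reading serving as both entry score and baseline, no concurrent control, a threshold that excludes some patients, and imperfect correlation between readings. The first two are in the plan; the last two are assumptions, though very plausible for "their average pain over the past 24 hours".

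Under the assumed ranges the spurious improvement is about 0.04 to 0.55 points, centrally 0.14 to 0.37, usually below the projected half-width. That is enough to make the nominal 95% interval misleading, but not to show that treatment has no effect. The change is worth making because it is cheap.

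**What to change.** 1. Use the Baseline-visit NRS for eligibility only. Repeat the one-question NRS at the Trial System Implant visit, before any lead is placed, and use that reading as the baseline.
2. Apply the new baseline to all NRS change endpoints: 6 months in section 6.1.1, and end of trial, 3, 12, 18 and 24 months in section 6.1.3. Changing only 6.1.1 would put the 6-month and other results on different baselines. Sections 4.3.1, 4.3.3, 5.3.2, 6.1.1 (Primary Endpoint) and 6.1.3 and Table 2 need matching edits.
3. State that the correction may be partial if readings days apart correlate more strongly than readings months apart.
4. Keep one primary estimate on all evaluable subjects, using the Baseline-visit reading where no second one exists. Reporting two separate sets would leave no single primary result and would widen each interval.
5. Add a regression-to-the-mean sensitivity analysis over assumed correlations, for example 0.5 to 0.9. The screening mean and SD must also be varied, or estimated from the truncated entry scores. Report it next to the primary estimate and carry it into the comparison with existing trials. It needs no new data and covers subjects already enrolled.

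The cost is one interview question at an existing visit, one CRF field, one amendment with notification of the ethics committees, some missing second readings and a slightly smaller reported change. No eligibility rule or treatment changes.
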